8.3.3 Follow-up of AEs and SAEs

After the initial AE/SAE report, the investigator is required to proactively follow each patient at subsequent visits/contacts. All SAE/non-serious AEs will be followed until resolution, stabilisation, the event is otherwise explained, or the patient is lost to follow-up

Any AEs that are unresolved at the patient's last AE assessment in the study are followed up by the investigator for as long as medically indicated, but without further recording in the eCRF. AstraZeneca retains the right to request additional information for any patient with ongoing AE(s)/SAE(s) at the end of the study, if judged necessary.

8.3.4 Adverse event data collection

The following variables will be collected for each AE:

- AE (verbatim)
- The date and time when the AE started and stopped
- Maximum intensity
- Whether the AE is serious or not
- Investigator causality rating against the IP(s) (yes or no)
- Action taken with regard to IP(s)
- AE caused patient's withdrawal from study (yes or no)
- Outcome.

In addition, the following variables will be collected for SAEs:

- Date AE met criteria for serious AE
- Date investigator became aware of serious AE
- AE is serious due to
- Date of hospitalisation
- Date of discharge
- Probable cause of death
- Date of death
- Autopsy performed
- Causality assessment in relation to study procedure(s)
- Causality assessment to other medication

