8.3.2 Time period and frequency for collecting AE and SAE information

Adverse events and SAEs will be collected from the time of signature of the ICF throughout the treatment period and including the follow-up period (Visit 14).

All SAEs will be recorded in the eCRF and reported to the sponsor or designee within 24 hours, as indicated in [Appendix C](#). The investigator will submit any updated SAE data to the sponsor within 24 hours of it being available.

Investigators are not obligated to actively seek AE or SAE in former study patients. However, if the investigator learns of any SAE, including a death, at any time after a patient's last visit and he/she considers the event to be reasonably related to the study treatment or study participation, the investigator may notify the sponsor.

The method of recording, evaluating, and assessing causality of AE and SAE and the procedures for completing and transmitting SAE reports are provided in [Appendix C](#).

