3.3.6.1 Adverse events (AEs)

Adverse events (including SAEs) experienced by the patients will be collected throughout the entire study and will be coded by the AstraZeneca designee using the latest version of the Medical Dictionary for Regulatory Activities (MedDRA).

Adverse event data will be categorized according to their onset date into the following study periods:

- AEs in the on-study period, defined as:

date of first dose of IP \leq AE onset date \leq study completion or withdrawal date.

- *AEs in the pre-treatment period (screening period) are defined as those with onset before the day of first dose of study treatment.* If any subject is re-screened, the latest available screening will be used for this purpose

If the AE has a completely missing (and unresolvable) onset date, then the AE will be assumed to be treatment-emergent, unless the end date indicates unambiguously that the AE resolved before treatment started. If the AE has a partially missing (and unresolvable) onset date, then the AE will also be assumed to be treatment-emergent, unless either the end date

indicates unambiguously that the AE resolved before treatment started, or the partial onset date is in the month/year prior to start of treatment.

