4.2.12.1 Adverse Events

All AEs experienced by the patients will be collected throughout the study, as per CSP Table 1, and will be coded by the AstraZeneca designee using the latest version of MedDRA.

The timings of AEs will be assigned to the period in which they occurred. AEs occurring during the screening period will be listed, but not summarised separately.

AEs or Serious Adverse Events (SAEs) will be categorised as occurring on-study period based on their onset date:

An overall summary table will be produced showing the number and percentage of patients with at least one AE in each of the following categories: any AEs, SAEs, AEs with outcome of death, and AEs leading to discontinuation of IP (DAEs). The total number of AEs in the different AE categories in terms of AE counts will also be presented (i.e. accounting for multiple occurrences of the same event in a patient).

AEs, SAEs, AEs with outcome of death, and DAEs will be summarised by SOC and PT assigned to the event using the MedDRA dictionary by descending frequency order in the overall benralizumab treatment group. For each PT, the number and percentage of patients reporting at least one occurrence of the event will be presented (i.e. subjects with multiple occurrences of the same PT will only be counted once). A summary of the most common (frequency of $>5\%$) AEs in any treatment group will be presented by PT.

AEs and SAEs will be summarized by PT and Investigator's causality assessment (related versus not related) and maximum intensity. If a patient reports multiple occurrences of the same AE within the same reported period, the maximum intensity will be taken as the highest recorded maximum intensity (the order being mild, moderate, and severe).

Separate listings of subjects with AEs, SAEs, AEs with outcome of death, or DAEs will be presented.

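### The SAP places AEs by onset date only, so a screening-onset AE that turns serious, fatal or treatment-stopping after dosing can be missed from the SAE, death and DAE summary tables

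*Protocol*

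**What the plan says.** **Collection.** Protocol 8.3.2 starts safety collection at consent: "Adverse events and SAEs will be collected from the time of signature of the ICF throughout the treatment period". Table 1 of the protocol puts screening at Days -28 to -14, and Protocol 4.1 allows it to be extended. AEs with onset before the first dose will therefore be in the database.

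**Fields.** Protocol 8.3.4 records for each AE "The date and time when the AE started and stopped", along with maximum intensity, the action taken with the product and the outcome. SAEs also carry "Date AE met criteria for serious AE" and, where relevant, a date of death.

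**Placement.** SAP 3.3.6.1 states: "Adverse event data will be categorized according to their onset date into the following study periods". The on-study period runs from the first dose to study completion or withdrawal, and onset before the day of first dose makes an AE pre-treatment. SAP 4.2.12.1 repeats the rule for serious events: "AEs or Serious Adverse Events (SAEs) will be categorised as occurring on-study period based on their onset date". It says of screening events: "AEs occurring during the screening period will be listed, but not summarised separately".

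**Output.** SAP 4.2.12.1 then specifies an overall table and tables by system organ class and preferred term for AEs, SAEs, fatal AEs and DAEs, with separate listings of each. No section uses the seriousness date, the date of death or the treatment-stop date to place an event in a period.

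**The concern.** An SAE, a fatal AE and a DAE are each defined by something that can happen well after onset. Onset date alone is a poor way to decide whether that outcome belongs to time on drug. For example, an AE that begins on Day -10 and leads to hospital admission or a treatment stop on Day 20 has its important consequence on benralizumab, yet the rule places it before treatment.

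The study has no control arm, and long-term safety is one of its stated purposes, so its main safety output is a set of small counts. Compared with a rule that also uses the date of the outcome, onset-only placement can only give equal or lower counts. It can also produce an internal mismatch: SAP 4.2.1 tabulates treatment discontinuations with their reasons, so an AE discontinuation could appear there with no matching entry in the DAE table.

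The SAP is cautious in a neighbouring case. SAP 3.3.6.1 treats an AE with a wholly missing onset date as treatment-emergent unless its end date clearly precedes treatment. It gives no similar protection to a fully dated AE that becomes serious on drug.

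**Working it through.** The documents give no figure on this point, so there is none to reproduce. The check applies the rule to test records and then sizes one affected child.

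**Rule as written.** Day 0 is the first dose (SAP 3.1.2). Let E be the day of study completion or withdrawal. An AE is on-study if 0 ≤ onset ≤ E.

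**Variant.** Let q be the day of the outcome that defines the table concerned (became serious, died, or stopped treatment). An AE is on-study if 0 ≤ onset ≤ E, or if onset < 0 and 0 ≤ q ≤ E.

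Test records, with E later than Day 20:

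| Onset day | q | SAP rule | Variant |
|---|---|---|---|
| -10 | 20 | pre-treatment | on-study |
| -10 | -5 | pre-treatment | pre-treatment |
| 5 | 20 | on-study | on-study |
| -1 | 0 | pre-treatment | on-study |

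The two rules differ only where onset precedes the first dose and the outcome does not.

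**Weight of one child.** The planned numbers are 30 evaluable children aged 6 to 11 years and at least 8 per weight stratum (SAP 1.3).

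- Overall: 1/30 = 3.3%.
- Minimum-size stratum: 1/8 = 12.5%.

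Exact (Clopper-Pearson) 95% limits show how the message of a table row changes. The SAP does not plan these intervals; they are given for scale only.

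- 0/30: upper limit 1 - 0.025^(1/30) = 11.6%.
- 1/30: lower limit 1 - 0.975^(1/30) = 0.1%. The upper limit solves (1-p)^30 + 30p(1-p)^29 = 0.025, giving 17.2%.
- 0/8: upper limit 1 - 0.025^(1/8) = 36.9%.
- 1/8: lower limit 1 - 0.975^(1/8) = 0.3%. The upper limit solves (1-p)^8 + 8p(1-p)^7 = 0.025, giving 52.7%.

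These denominators are planned evaluable numbers. The safety analysis set may be larger, which would make each percentage a little smaller.

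**The case against.** **The event is not lost.** A reader might infer that it vanishes from the report. The documents do not support that. SAP 4.2.12.1 requires listings of AEs, SAEs, fatal AEs and DAEs with no stated period limit, and SAP 4.2.1 tabulates treatment stops with reasons. In a study of about 33 children, one case would be easy to find. This stands, and it limits the harm to the summary tables.

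**The recording convention is not visible.** A reader might take the separate seriousness date in Protocol 8.3.4 as proof that a worsening AE stays on one record. It is not proof: the field is equally useful when onset and seriousness both follow dosing. Protocol 8.3.2 leaves recording methods to Appendix C, which is not in the text available here. Protocol 8.3.7 and SAP 3.3.6.5 have aggravated examination findings reported as AEs. If sites open a new record for any worsening, its onset is post-dose and the SAP counts it. The point is therefore conditional on a single record.

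**The exclusion is not spelled out.** The table specifications do not say on-study only, and the sentence on screening AEs could mean only that they get no table of their own. Exclusion is still the more natural reading, because the onset rule comes immediately before the tables. If pooling was intended, the SAP should say so.

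**Cases will be rare.** Exclusion criteria 2, 5 and 7 (Protocol 5.2) and the postponement of dosing for intercurrent illness or fever (Protocol 6.3.4) remove many candidates. SAP Appendix I sets an onset with a missing day in the month of first dose to the first-dose day, so that AE counts as on-study. These limits stand, but they rest partly on investigator judgement and do not rule the case out.

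None of these arguments brings a fully dated, single-record case into the tables.

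**Conclusion.** The point holds in a limited form. Under SAP 3.3.6.1 and 4.2.12.1, an AE with a complete pre-dose onset date that stays on one record and turns serious, fatal or treatment-stopping after the first dose is classed as pre-treatment. On the natural reading it is then left out of the on-study SAE, fatal-AE and DAE counts. This rests on two assumptions: that worsening is kept on the same record, and that the tables cover on-study events only.

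The size per case is 3.3 percentage points of 30 children, or 12.5 points of a stratum of 8. The number of cases cannot be derived from the documents. A reader might try to size it from an AE rate. Assuming 2 to 6 AEs per child-year, 33 children would have between 33 × 2 × 14/365.25 = 2.5 and 33 × 6 × 28/365.25 = 15.2 AEs starting in 14 to 28 days of screening. That rate is not in the documents, and the result counts all screening-onset AEs, most of which would never qualify. It does not measure this problem.

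The point affects safety reporting only. The study tests no hypothesis, so no error rate or sample size is involved. It is minor and likely to arise seldom.

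**What to change.** Add one rule to SAP 3.3.6.1 and repeat it in 4.2.12.1. Also count as on-study any AE with onset before the first dose that, on or after the first dose and within the on-study period, does one of the following:

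- meets a seriousness criterion, dated by the seriousness field in Protocol 8.3.4;
- is fatal, dated by the date of death;
- leads to discontinuation of the product, identified from the action-taken field.

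The same edit should state that the SAE, fatal-AE and DAE summaries cover on-study events as so defined. That settles the ambiguity about screening AEs and helps the DAE table agree with disposition.

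The cost is a sentence or two of SAP text and a small programming change, with no new data. The safety counts may become slightly less favourable. New recording guidance for sites is not proposed: this SAP edition was approved in October 2022, after the protocol's estimated last-patient completion of September 2022, so guidance would probably come too late.

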8.3.5 Causality collection

The investigator will assess causal relationship between IP and each AE, and answer 'yes' or 'no' to the question 'Do you consider that there is a reasonable possibility that the event may have been caused by the IP?'

For SAEs, causal relationship will also be assessed for other medication and study procedures. Note that for SAEs that could be associated with any study procedure the causal relationship is implied as 'yes'.

A guide to the interpretation of the causality question is found in [Appendix C](#) to the CSP.

8.3.6 Adverse events based on signs and symptoms

All AEs spontaneously reported by the patient or care provider or reported in response to the open question from the study site staff: 'Have you/the child had any health problems since the previous visit/you were last asked?' or revealed by observation will be collected and recorded in the eCRF. When collecting AEs, the recording of diagnoses is preferred (when possible) to recording a list of signs and symptoms. However, if a diagnosis is known and there are other signs or symptoms that are not generally part of the diagnosis, the diagnosis and each sign or symptom will be recorded separately.

8.3.7 Adverse events based on examinations and tests

The results from the CSP mandated laboratory tests and vital signs will be summarised in the clinical study report (CSR). Deterioration as compared to baseline in protocol-mandated laboratory values and vital signs should therefore only be reported as AEs if they fulfil any of the SAE criteria or are the reason for discontinuation of treatment with the IP.

If deterioration in a laboratory value/vital sign is associated with clinical signs and symptoms, the sign or symptom will be reported as an AE and the associated laboratory result/vital sign will be considered as additional information. Wherever possible the reporting investigator uses the clinical, rather than the laboratory term (eg, anaemia versus low haemoglobin value). In the absence of clinical signs or symptoms, clinically relevant deteriorations in non-mandated parameters should be reported as AE(s).

Any new or aggravated clinically relevant abnormal medical finding at a physical examination as compared with the baseline assessment will be reported as an AE unless unequivocally related to the disease under study, see Section 8.3.8.

8.3.8 Disease-under study (DUS)

Symptoms of the DUS are those which might be expected to occur as a direct result of asthma. Events which are unequivocally due to the disease under study should not be reported as an AE during the study unless they meet SAE criteria or lead to discontinuation of the IP.

8.4 Safety reporting and medical management

8.4.1 Reporting of serious adverse events

All SAEs have to be reported, whether or not considered causally related to the IP, or to the study procedure(s). All SAEs will be recorded in the eCRF.

If any SAE occurs in the course of the study, then investigators or other site personnel inform the appropriate AstraZeneca representatives within one day ie, immediately but **no later than 24 hours** of when he or she becomes aware of it.

The designated AstraZeneca representative works with the investigator to ensure that all the necessary information is provided to the AstraZeneca Patient Safety data entry site **within 1 calendar day** of initial receipt for fatal and life-threatening events **and within 5 calendar days** of initial receipt for all other SAEs.

For fatal or life-threatening AEs where important or relevant information is missing, active follow-up is undertaken immediately. Investigators or other site personnel inform AstraZeneca representatives of any follow-up information on a previously reported SAE within one calendar day ie, immediately but **no later than 24 hours** of when he or she becomes aware of it.

Once the investigators or other site personnel indicate an AE is serious in the electronic data capture (EDC) system, an automated email alert is sent to the designated AstraZeneca representative.

If the EDC system is not available, then the investigator or other study site staff reports a SAE to the appropriate AstraZeneca representative by telephone.

The AstraZeneca representative will advise the investigator/study site staff how to proceed.

For further guidance on the definition of a SAE, see [Appendix C](#) of the CSP.

8.4.2 Pregnancy

All pregnancies and outcomes of pregnancy should be reported to AstraZeneca.

If a pregnancy is reported, the investigator should inform the sponsor within 24 hours of learning of the pregnancy.

Abnormal pregnancy outcomes (eg, spontaneous abortion, foetal death, stillbirth, congenital anomalies, ectopic pregnancy) are considered SAEs.

8.4.2.1 Maternal exposure

If a patient becomes pregnant during the study, IP should be discontinued immediately.

Pregnancy itself is not regarded as an AE unless there is a suspicion that the IP under study may have interfered with the effectiveness of a contraceptive medication. Congenital abnormalities/birth defects and spontaneous miscarriages should be reported and handled as SAEs. Elective abortions without complications should not be handled as AEs. The outcome of all pregnancies (spontaneous miscarriage, elective termination, ectopic pregnancy, normal

birth or congenital abnormality) should be followed up and documented even if the patient was discontinued from the study.

If any pregnancy occurs in the course of the study, then the investigator or other site personnel informs the appropriate AstraZeneca representatives within 1 day ie, immediately but **no later than 24 hours** of when he or she becomes aware of it.

The designated AstraZeneca representative works with the investigator to ensure that all relevant information is provided to the AstraZeneca Patient Safety data entry site within 1 or 5 calendar days for SAEs (see Section [8.3.2](#)) and within 30 days for all other pregnancies.

The same timelines apply when outcome information is available.

8.4.2.2 Paternal exposure

There is no restriction on fathering children or donating sperm during the study. However, information on a pregnancy of a partner will be collected.

8.4.3 Overdose

For this study, any dose of benralizumab greater than 200 mg will be considered an overdose.

There is no specific treatment for an overdose with benralizumab. If overdose occurs, the patient should be treated supportively with appropriate monitoring as necessary.

- An overdose with associated AEs is recorded as the AE diagnosis/symptoms on the relevant AE modules in the eCRF and on the Overdose eCRF module.
- An overdose without associated symptoms is only reported on the Overdose eCRF module

If an overdose on an AstraZeneca study drug occurs in the course of the study, then the investigator or other site personnel inform appropriate AstraZeneca representatives immediately, or **no later than 24 hours** of when he or she becomes aware of it.

The designated AstraZeneca representative works with the investigator to ensure that all relevant information is provided to the AstraZeneca Patient Safety data entry site.

For overdoses associated with a SAE, the standard reporting timelines apply, see Section [8.4.1](#). For other overdoses, reporting must occur within 30 days.

8.4.4 Management of investigational product-related reaction

Appropriate drugs (eg, epinephrine, H1 and H2 antihistamines, and corticosteroids), and medical equipment to treat acute anaphylactic reactions must be immediately available at the clinical research site where IP is administered. Study personnel must be trained to recognize

and treat anaphylaxis ([Laviolette et al 2013](#), [Lieberman et al 2010](#)). Details on anaphylaxis management are provided in [Appendix F](#).

Anaphylaxis will be defined as a serious reaction that is rapid in onset (minutes to hours) and that may result in death ([Sampson et al 2006](#)). Anaphylaxis to an IP that the patient has not been previously exposed to (such as benralizumab) is deemed highly likely when Sampson criterion 1 is fulfilled. Sampson criteria 2 and 3 are also listed for completeness:

1. The acute onset of a reaction (minutes to hours) with involvement of the skin, mucosal tissue, or both, AND AT LEAST 1 of the following: a) respiratory compromise or b) reduced BP or symptoms of end-organ dysfunction.
2. Two or more of the following that occur rapidly after exposure to a likely allergen for that patient including: involvement of the skin/mucosal tissue, respiratory compromise, reduced BP or associated symptoms and/or persistent gastrointestinal symptoms.
3. Reduced BP after exposure.

Patients will have had a pre-assessment (ie, vital signs) prior to IP administration and the sponsor recommends that patients should be observed after IP administration for a minimum of 1 hour for the appearance of any acute drug reactions.

Serum tryptase or other blood or urine testing relevant to the diagnosis of anaphylaxis may be obtained at a local lab at the discretion of the investigator.

8.4.5 Medication error

If a medication error occurs in the course of the study, then the investigator or other site personnel informs the appropriate AstraZeneca representatives within 1 day (ie, immediately but no later than 24 hours) of when he or she becomes aware of it.

The designated AstraZeneca representative works with the investigator to ensure that all relevant information is completed within 1 (Initial Fatal/Life Threatening or follow-up Fatal/Life Threatening) or 5 (other serious initial and follow-up) calendar days if there is an SAE associated with the medication error (see Section [8.3.2](#)) and within 30 days for all other medication errors.

The definition of a Medication Error can be found in [Appendix C](#).

8.4.6 Medical device deficiencies

Medical devices (APFSs) are being utilised to deliver the IMP under study. In order to fulfil regulatory reporting obligations worldwide, the investigator is responsible for the detection and documentation of events meeting the definitions of medical device deficiency that occur during the study with such medical devices.

The definition of a Medical Device deficiency can be found in [Appendix G](#).

NOTE: Incidents and deficiencies fulfilling the definition of an AE/SAE will also follow the processes outlined in [Appendix G](#) of the protocol.

